9.3.1 Inclusion Criteria

Subjects must meet all of the following criteria to be included in this study:

Core Study

1. MCI due to AD or Mild AD according to the National Institute of Aging – Alzheimer’s Association (NIA-AA) core clinical criteria and must have all of the following at Screening: (revised per Amendment 04)
 - a. MMSE score equal to or greater than 24
 - b. CDR global score of 0.5
 - c. CDR Memory Box score of 0.5 or greater
2. A history of subjective memory decline with gradual onset and slow progression over the last 1 year before Screening; this MUST be corroborated by a study partner
3. Cognitive impairment of at least 1 SD from age-adjusted norms in total recall or delayed recall on the ISLT.
4. Positive biomarker for brain amyloid pathology as indicated by at least 1 of the following:
 - a. PET assessment of amyloid imaging agent uptake into brain. Note: amyloid PET screens will be performed according to local regulatory guidelines and thus may be restricted for those subjects who are not suitable for LP to obtain CSF for testing of eligibility.
 - b. CSF AD assessment (eg, tau: A β (1-42) ratio) (revised per Amendment 04)

NOTE: Subjects may undergo both the amyloid PET and CSF assessments, but need a positive amyloid result in only 1 of the 2 procedures to confirm eligibility. Subjects who consent to amyloid PET or CSF for eligibility purposes are not required to participate in the amyloid PET or CSF longitudinal substudies. Use of a historical amyloid positive PET (conducted within 12 months before the planned date of randomization) is acceptable for determination of eligibility but will not suffice for the baseline assessment if the subject wishes to consent to the amyloid PET longitudinal substudy. The historical imaging data must be made available to the sponsor. Historical CSF samples, if collected, processed, and stored under appropriate conditions and approved by the sponsor, may be analyzed to determine CSF amyloid positivity. (revised per Amendments 04 and 06).
5. Male or female subjects between 50 and 85 years of age, inclusive at the time of consent
6. If receiving an AChEI or memantine or both for AD, must be on a stable dose for at least 12 weeks before Randomization. Treatment-naïve subjects with AD can be entered into the study.

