9.7.1.1.2 SECONDARY ENDPOINTS

The key secondary endpoints of the study are as follows (revised per Amendment 06):

- Change from baseline in ADCOMS at 24 months in the combined studies
- Change from baseline in amyloid PET SUVR at 24 months for brain amyloid levels in the combined studies
- Change from baseline in amyloid PET SUVR at 24 months for brain amyloid levels in the individual studies

The other secondary endpoints of the study are as follows (revised per Amendment 06):

- Change from baseline in the CDR-SB at 24 months for subjects enriched by baseline PET SUVR, eg, between 1.2 and 1.6, in the combined studies
- Change from baseline in the ADCOMS at 24 months for subjects enriched by baseline PET SUVR, eg, between 1.2 and 1.6, in the combined studies
- The rate of change over time (mean slope) based on CDR-SB score over 24 months in the combined studies
- Time to worsening of CDR scores by 24 months (eg, the worsening of global CDR score is defined as an increase from baseline by at least 0.5 points on the global CDR scale on 2 consecutive scheduled visits at which global CDR is undertaken) in the combined studies
- Time to conversion to dementia by 24 months for subjects who were not clinically staged as dementia at Baseline based on clinical diagnosis in the combined studies (revised per Amendment 01)
- Change from baseline in CDR-SB at 27 months (ie, 24 months of treatment plus 3 months posttreatment follow-up) in the combined studies (revised per Amendment 01)
- Change from baseline in ADAS-cog14, MMSE, and FAQ at 24 months in the combined studies
- Change from baseline in ADAS-cog14 Word List (immediate recall and delayed recall) at 24 months in the combined studies (revised per Amendment 01)

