9.7.1.6.1 PRIMARY EFFICACY ANALYSIS

The primary analysis will be based on an intent to treat philosophy without regard to adherence to treatment. The primary analysis of the change from baseline in CDR-SB at 24 months will be performed to compare elenbecestat 50 mg per day versus placebo using a linear mixed effects model for repeated measures (MMRM) on the FAS. The MMRM model will include fixed effects of treatment group, visit, treatment group by visit interaction, baseline CDR-SB, baseline CDR-SB by visit interaction, and randomization stratification variables (ie, region [7 levels], clinical dementia [yes, no], and concurrent AD medication use at randomization [Visit 2] [yes, no]). *ApoE4* status may be included in the model if appropriate. (revised per Amendments 01, 02, and 06) An unstructured covariance matrix will be employed to model the covariance of within subject effect; if MMRM fails to converge then a covariance structure with fewer parameters from the following list will be employed according to the prespecified order in the list until the MMRM converges. The list of covariance structure will include Heterogeneous Toeplitz, Toeplitz, Heterogeneous Compound Symmetry, and Compound Symmetry. This primary analysis will include all observed post baseline data of the change from baseline in CDR-SB without imputation of missing values. The treatment effect for elenbecestat versus placebo will be compared at 24 months based on MMRM model. The LS means and difference in LS means between elenbecestat treatment group and placebo, and corresponding 95% CI will be presented.

The null hypothesis is that there is no difference in the mean change from baseline in CDR-SB at 24 months between elenbecestat 50 mg per day and placebo. The corresponding alternative hypothesis is that there is a difference in the mean change from baseline in CDR-SB at 24 months between elenbecestat 50 mg per day and placebo.

The primary analysis will be repeated to minimize the impact of change in concomitant AD medications where efficacy data after initiation of new AD medications and increase of current AD medications will be censored.

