Time to worsening of CDR scores by 24 months will be analyzed on the FAS using Cox regression model for treatment effect adjusting for randomization stratification factors. *ApoE4* status may be included in the model if appropriate. (revised per Amendment 06) Time to worsening of a CDR score is defined as time from randomization to worsening of the CDR score (ie, the first worsening in 2 consecutive scheduled visits). For subjects whose CDR scores have not worsened by the end of the Treatment Period of the Core Study, the time to worsening of the CDR score will be censored at the date of last CDR assessment for these subjects.

Time to conversion to dementia for subjects who were not clinically staged as dementia at Baseline based on clinical diagnosis will be analyzed on the FAS using Cox regression model for treatment effect adjusting for randomization stratification factors. *ApoE4* status may be included in the model if appropriate. (revised per Amendment 06) Proportion of subjects with

dementia diagnosis at 24 months will be estimated using Kaplan—Meier method based on time to conversion to dementia based on clinical diagnosis. Time to conversion to dementia for subjects who were not clinically staged as dementia at Baseline based on clinical diagnosis is defined as time from randomization to conversion to dementia based on clinical diagnosis. For subjects without clinical dementia by the end of study, the time to conversion to dementia based on clinical diagnosis will be censored at the date of last dementia diagnosis.

The other continuous secondary efficacy endpoints as defined above will be analyzed using the same MMRM model as the primary efficacy analysis to compare elenbecestat 50 mg per day versus placebo on the FAS, using baseline value corresponding to the response variable in the model.

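### Free improvement: the Cox models for CDR worsening and dementia conversion omit baseline CDR-SB, which every subject has and the protocol's other CDR-SB models use

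*Protocol*

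**What the plan says.** Protocol section 9.7.1.6.2 writes out both time-to-event models. For CDR worsening: "Time to worsening of CDR scores by 24 months will be analyzed on the FAS using Cox regression model for treatment effect adjusting" for the stratification factors. The second analysis is of "Time to conversion to dementia for subjects who were not clinically staged as dementia at Baseline", and it too, "based on clinical diagnosis will be analyzed on the FAS using Cox regression model for treatment effect adjusting for randomization stratification factors". Either model may also take in ApoE4. No other covariate is named.

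The strata are listed in section 9.7.1.6.1: "region [7 levels], clinical dementia [yes, no], and concurrent AD medication use at randomization [Visit 2] [yes, no". Section 9.7.1.1.2 gives, as an example of CDR worsening, "an increase from baseline by at least 0.5 points on the global CDR scale on 2 consecutive scheduled visits". Inclusion criterion 1 in section 9.3.1 requires, at Screening, a "CDR global score of 0.5".

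The other models differ:
- The primary MMRM (9.7.1.6.1) contains "baseline CDR-SB, baseline CDR-SB by visit interaction, and randomization stratification variables".
- The ANCOVA after multiple imputation (9.7.1.6.1) and the slope model (9.7.1.6.2) also carry baseline CDR-SB.
- The remaining continuous secondary endpoints each use their own baseline value.

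Section 9.1.2.1 places the baseline CDR at Visit 2, before the first dose, for all subjects.

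**The concern.** Selection at global CDR 0.5 leaves little spread in the global score at entry. The sum of boxes is the finer severity measure, and it is already in the database for everyone.

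In the CDR-worsening model, severity enters only through the yes/no dementia stratum, with at most about 25% of subjects on the yes side (section 9.1). In the conversion model that stratum is essentially constant, because subjects staged as having dementia at Baseline are left out. Only region and AD medication remain (plus ApoE4, if added), and neither measures severity.

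The Cox model differs from linear regression here. Leaving out a prognostic covariate pulls the estimated hazard ratio toward 1 even under perfect randomization, and power falls with it. Section 8.2 lists both endpoints as superiority objectives for the pooled studies.

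**Working it through.** **1. The plan's own sample size (section 9.7.2).** Inputs: placebo change 1.46, SD 2.05, 25% reduction, two-sided alpha 0.05, power 90%, dropout 30%.
- Difference = 0.25 × 1.46 = 0.365.
- n per arm = 2 × (1.960 + 1.282)² × 2.05² / 0.365² = 663.
- With dropout: 663 / 0.70, rounded up, is 948 per arm, or 1896 in total.

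The stated 1900 is reproduced. It concerns the primary t-test only. The protocol gives no event rate, hazard ratio or power for either Cox endpoint, so everything in steps 2 to 4 rests on assumptions.

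**2. Simulation set-up (assumed).**
- Hazard = h0 × exp(b × treatment + g × x), where x is standardized baseline CDR-SB.
- Treatment hazard ratio exp(b) = 0.80.
- exp(g), the hazard ratio per SD of baseline CDR-SB, = 1.3, 1.6, 2.0 or 2.5.
- h0 is set so that 24-month placebo risk is 25% or 40%.
- Exponential loss of 30% over 24 months; 600 trials per setting.
- CDR worsening: N = 1900. A 25% dementia stratum, with latent correlation 0.5 to x, stays in both models.
- Conversion: N = 0.75 × 1900 = 1425, with no dementia stratum.
- Region and AD medication are left out of both.

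**3. Power (%) without → with baseline CDR-SB.**

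| Endpoint | Risk | HR/SD 1.3 | 1.6 | 2.0 | 2.5 |
|---|---|---|---|---|---|
| CDR worsening | 25% | 55.7→57.7 | 50.3→53.0 | 55.8→61.2 | 46.0→55.8 |
| CDR worsening | 40% | 76.2→77.2 | 73.0→75.5 | 67.5→75.2 | 65.3→78.8 |
| Conversion | 25% | 44.8→46.2 | 43.8→43.5 | 39.3→45.0 | 41.3→46.2 |
| Conversion | 40% | 66.7→68.3 | 57.2→60.0 | 55.5→64.7 | 52.8→63.7 |

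Gains in points, by prognostic strength:
- HR 1.3–1.6 per SD: −0.3 to 2.8, so about 0–3.
- HR 2.0: 5.4 to 9.2, so about 5–9.
- HR 2.5: 4.9 to 13.5, so about 5–14.

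The Monte Carlo standard error of one power figure is about 2 points (√(0.25/600) = 0.020). Small differences should therefore not be over-read.

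**4. Hazard ratio.** Without the covariate, the estimate drifts from the true 0.80 to as far as 0.83. With it, the estimate stays between about 0.80 and 0.81.

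**Check.** Schoenfeld's formula for 369 events at HR 0.80 gives |ln 0.80| × √(369/4) − 1.96 = 0.18, or 57% power. This agrees with the 57.7% simulated with the covariate at HR 1.3 per SD.

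**The case against.** Adjusting a Cox model for the randomization strata is conventional, and a time-to-event response has no baseline value of its own in the way a change score has. The shift in the hazard ratio is at most about 0.03, and part of it reflects a more conditional estimand rather than the removal of bias. All of this stands, and it makes the point an efficiency gain rather than an error. It does not make the point a detail left to the SAP, because the protocol writes these models out down to an optional covariate.

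Two stronger readings are tempting.

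- **CDR-SB as distance to the event.** A reader might infer that baseline CDR-SB largely fixes how far each subject is from the event, since all enter at global CDR 0.5. The documents do not say so. Section 9.2.1 describes the global score as coming from its own algorithm, and no CDR-SB cut-off is given. The entry criterion applies at Screening, and Visit 2 can come weeks later (up to 50 days plus 30, section 9.1), so the baseline global score need not still be 0.5. The event definition is itself only an example. A simulation that equates global CDR 1 with CDR-SB of 4.5 or more gives gains of 6 to 18 points, but it builds the link in. Its log hazard ratios of 0.9 to 1.3 per SD mean hazard ratios of about 2.5 to 3.7, and it covers CDR worsening only.
- **The same loss for conversion.** Conversion is a clinical diagnosis with central review, not a function of the CDR boxes. The link to baseline CDR-SB is less direct, and a nil gain is possible.

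**Conclusion.** The point holds as a free improvement. The omission and the direction of its effect follow from the protocol's text and from a known property of the Cox model.

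The size does not follow from the documents. Over assumed hazard ratios of 1.3 to 2.5 per SD it runs from about 0 to 14 power points, and it is modest unless baseline CDR-SB is strongly prognostic (about 2 or more per SD). The larger gains are more plausible for CDR worsening, because the global score and the sum of boxes come from the same six domains.

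A reader might infer that the trial's conclusions are at risk, but they are not. Section 9.7.1.1.2 lists both endpoints as other secondary, and section 9.7.1.6.2 applies sequential testing to the key secondary endpoints only. The primary analysis and its type I error are unaffected.

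**What to change.** In section 9.7.1.6.2, prespecify continuous baseline (Visit 2) CDR-SB as a covariate, beside the stratification factors, in the Cox models for time to worsening of CDR and time to conversion to dementia. Carry the same line into the SAP before unblinding; added later, it would be post hoc.

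The cost is one sentence and no new data. The only downside is that the hazard ratio becomes conditional on baseline CDR-SB; unadjusted Kaplan–Meier curves can still be shown. Removing the constant dementia stratum from the conversion model would be cosmetic, since a constant contributes nothing to the fit, and it is not needed.

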9.1.4 End of Study

The end of the Core Study will be the date of the last study visit (Visit 15) for the last subject in the double-blind Randomization Phase. The end of the Extension Phase will be the date of the last study visit for the last subject enrolled in the Extension Phase. (revised per Amendments 03 and 06)

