9.7.1.6.3 EXPLORATORY EFFICACY ANALYSES

Time to change of concomitant AD treatment will be analyzed similarly to that for time to conversion to dementia based on clinical diagnosis. Time to change of concomitant AD treatment is defined as time from randomization to the first dose increase and/or initiation of treatment with AChEI or memantine after randomization. For subjects without any change of concomitant AD treatment by the end of study, the time to change of concomitant AD treatment will be censored at the date of last assessment of concomitant medication.

The proportion of subjects with any change of concomitant AD treatment at 24 months will be analyzed similarly to that for proportion of subjects with dementia diagnosis at 24 months.

The rate of change over time (mean slope) based on change from baseline in the NPI-10 item will be analyzed in a manner similar to that used for the rate of change over time (mean slope) based on change from baseline in the CDR-SB.

The analysis of the following exploratory efficacy endpoints will be performed to compare elenbecestat versus placebo using the appropriate prespecified statistical methods including MMRM model, analysis of covariance model (ANCOVA), etc. For each exploratory efficacy endpoint, the treatment effect for elenbecestat 50 mg per day versus placebo will be tested at a significance level of 2-sided alpha = 0.05.

- Change from baseline in NPI-10 item at 24 months

- Change from baseline in EQ-5D (subject self-reported, study partner self-reported, and subject measured by proxy) and QOL-AD (subject and study partner) at 24 months
- Change from baseline in Zarit's Burden Interview at 24 months

Additional analyses may be performed as needed.

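### Time to dementia conversion and time to change of AD treatment are defined by 24 months, but their analysis rules run to an undefined end of study, so the Cox models can count events after Month 24

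*Protocol*

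**What the plan says.** Section 9.7.1.1.2 lists the endpoint as "Time to conversion to dementia by 24 months for subjects who were not clinically staged as dementia at Baseline based on clinical diagnosis". Section 9.7.1.1.4 gives time to change of concomitant AD treatment the same 24-month limit.

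The analysis text is wider. In Section 9.7.1.6.2 the conversion time is "defined as time from randomization to conversion to dementia based on clinical diagnosis", with no upper limit, and the censoring sentence begins "For subjects without clinical dementia by the end of study"; the censoring date is that of the last dementia diagnosis. Section 9.7.1.6.3 has the matching sentence for AD treatment, "For subjects without any change of concomitant AD treatment by the end of study", with censoring at the last assessment of concomitant medication.

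The neighbouring rule for time to worsening of CDR is worded differently: "For subjects whose CDR scores have not worsened by the end of the Treatment Period of the Core Study". It then censors at the date of the last CDR assessment.

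On when the study ends, Section 9.1.4 says "The end of the Core Study will be the date of the last study visit (Visit 15") and ties this to the last subject. Appendix 5 places the end of the study at the last subject's final Extension Phase visit. Neither is a per-subject date.

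Table 5 marks disease staging at Visits 6 to 13, at early discontinuation and at Visit 15. It marks concomitant medications at every visit, including Visits 14 and 15.

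**The concern.** A completer first staged as demented at Visit 15 is an event under Section 9.7.1.6.2 and not an event under Section 9.7.1.1.2. Both cannot be followed. The same holds for a subject whose AD medication is first started or increased between Month 24 and Month 27.

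This is more than detail left to the SAP. The protocol has already written the censoring rule, and the rule disagrees with its own endpoint. Left alone, the analyst has two prespecified windows to choose between. The Cox hazard ratio would also cover longer follow-up than the Kaplan-Meier proportion reported beside it, which is read at 24 months. Where the protocol wants a Month 27 answer, it names a separate endpoint (CDR-SB at 27 months), so an unannounced extension of the conversion window looks unintended.

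**Working it through.** The protocol gives no event count, hazard ratio or power for either endpoint, so there is no stated figure to reproduce. The check compares the texts and then illustrates the size.

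**Windows side by side**

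| Endpoint | Endpoint list | Analysis rule |
|---|---|---|
| Conversion to dementia | by 24 months | no limit on event; end of study |
| Change of AD treatment | by 24 months | no limit on event; end of study |
| CDR worsening | by 24 months | end of Treatment Period, censored at last CDR assessment |

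**Timing (Table 5).** Visit 13 is Day 729 and Visit 15 is Day 813 for a completer: 813 − 729 = 84 days = 12 weeks. A subject who stops drug early also has Visit 15 at 12 weeks after the last dose. It falls after Day 729 if the last dose is later than Day 729 − 84 = Day 645, a little after Month 21 (Visit 12, Day 638). Post-Month-24 stagings therefore come from completers and from late stoppers.

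**Size for conversion.** The protocol gives no conversion rate, so these are assumptions: constant hazard λ = −ln(1 − p)/24, where p is conversion by Month 24.

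*(a) Two equal arms, no dropout, p = placebo conversion, on-drug HR 0.75.* Events by Month 24 per subject are p on placebo and 1 − (1 − p)^0.75 on drug. Events from Month 24 to 27 are (1 − p)(1 − e^(−3λ)) on placebo and (1 − p)^0.75 (1 − e^(−3hλ)) on drug, where h is the off-drug HR.

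For p = 0.35, λ = 0.01795. Events by Month 24 sum to 0.3500 + 0.2761 = 0.6261.
- h = 0.75: later events 0.0341 + 0.0287 = 0.0628; share 0.0628/0.6889 = 9.1%.
- h = 1: later events 0.0341 + 0.0380 = 0.0721; share 0.0721/0.6982 = 10.3%.

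| p | Share, effect persists | Share, effect vanishes | Event-weighted HR if it vanishes |
|---|---|---|---|
| 0.20 | 10.0% | 11.3% | 0.775 |
| 0.35 | 9.1% | 10.3% | 0.773 |
| 0.50 | 8.0% | 9.1% | 0.770 |

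The HR column is exp[(1 − share) × ln 0.75]. If the effect persists, the HR stays at 0.750.

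*(b) With dropout.* Take 0.75 × 1900 = 1425 subjects without dementia at baseline (from the approximate 25% cap on mild dementia), 30% dropout spread uniformly over 24 months, no staging after stopping, and one common hazard with S(t) = e^(−λt). Extra events = 1425 × 0.7 × [S(24) − S(27)]. Events by Month 24 = 1425 × {0.7p + 0.3[1 − p/(24λ)]}.

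For p = 0.35: extra = 1425 × 0.7 × (0.6500 − 0.6159) = 34. Events by Month 24 = 1425 × (0.2450 + 0.0563) = 429. Share = 34/463 = 7.3%.

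For p = 0.25 and 0.45 the extra events are about 26 and 40, with shares of 8.0% and 6.6%. With the effect vanishing, the HR is 0.76 to 0.77. At p = 0.50 the share falls to 6.3%.

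No size was computed for change of AD treatment.

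**The case against.** Several stronger readings are tempting, and the documents do not bear them out.

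- *The analysis fails the stated 24-month objective.* The dementia objective in Section 8.2 has no 24-month limit. The window comes from the endpoint list, so the conflict is with the endpoint.
- *Off-drug events come only from completers, and a 24-month cut makes the comparison on-treatment.* Early stoppers are also staged at their own Visit 15, and conversions seen there before Month 24 stay in the model after any 24-month cut. That fits the intent-to-treat approach of Section 9.7.1.6.1.
- *Section 9.1.4 fixes a Month 27 cut-off for each subject.* It defines a trial-level date. The charge that stands is an undefined term that conflicts with the endpoint.
- *Open-label Extension events would enter the Core analysis.* The Appendix 5 sentence makes the term ambiguous, but Section 9.7 sends Extension methods to that appendix, which has its own conversion endpoint.
- *The CDR rule is already right.* Its date of last CDR assessment can be Visit 14 or 15, since Table 5 schedules CDR at both.

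It is also fair to say that the Kaplan-Meier proportions at 24 months are untouched, that these endpoints lie outside the key secondary sequence, and that the shift to about 0.77 needs the drug effect to disappear at once on stopping. All of this limits the consequence. None of it removes the contradiction between Sections 9.7.1.1.2 and 9.7.1.6.2, or between 9.7.1.1.4 and 9.7.1.6.3.

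**Conclusion.** The contradiction is real and worth correcting before unblinding, with modest consequences. As written, the two Cox models take in events after Month 24 that the endpoint definitions exclude.

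For conversion the excess is roughly 7% to 11% of events across the two sets of assumptions, and about 6% at the extreme of 50% conversion with 30% dropout. These shares rest on constant hazard and on assumed conversion rates that the protocol does not supply. An assumed hazard ratio of 0.75 does not move if the effect persists off drug, and reads about 0.76 to 0.78 if it vanishes immediately. A reader should not infer that the conversion result would be materially biased, or that any primary or key secondary conclusion is at risk.

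**What to change.** In Sections 9.7.1.6.2 and 9.7.1.6.3, replace the end-of-study wording with one date limit: the upper end of the Month 24 visit window, timed from randomization. With the ±10 days that Table 5 allows for Visit 13, that is Day 729 + 10 = Day 739. Count only events on or before it, whether or not the subject is still on drug. Censor all others at their last disease staging, or last concomitant medication assessment, on or before the same point.

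Apply the same limit to the censoring date in the CDR-worsening rule, so that all three time-to-event analyses share one window. If Month 27 staging is of interest, summarise it separately.

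The cost is a short wording change carried into the SAP, no new data, and slightly fewer events: for conversion, the share shown above.
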